### 5.2.1 Procedures for Screening and Enrolment - Visit 1 (Day -14 (-14 days/ +3 days))

A signed and dated informed consent form will be obtained before screening procedures. After informed consent is obtained, subjects who are screened will be allocated a subject number. All screened subjects must be identifiable throughout the study. The investigator will maintain a list of subject numbers and names to enable records to be found at a later date if required.

#### 5.2.1.1 Screening – Visit 1 - Day -14 (-14 days/ +3 days)

The Screening Visit (Visit 1) will take place on Day -14 of the study. The visit window will be from Day -28 to Day -11.

The following assessments will be performed:

- Eligibility check (inclusion/exclusion criteria)
- Demographic data (year of birth, age, sex, ethnicity, and race)
- Medical history, including significant ongoing medical history, surgical history and vulvodynia history
- Vital signs (supine or sitting blood pressure and heart rate)
- Body height and weight
- Physical examination
- Blood sampling (nonfasting) for haematology, biochemistry, putative antibodies and FSH

- Urine pregnancy test
- Urine test for illicit drugs
- Vaginal culture/polymerase chain reaction for yeast, parasitic and bacterial infections
- PCS
- mFSFI (pain to be recorded at the visit, and 1 week prior to the Baseline Visit; other domains to be recorded only at the visit)
- Relationship/partner status (to be recorded at the visit and then weekly during the screening period)
- mVPAQ (pain and life interference to be recorded at the visit, and 1 week prior to the Baseline Visit; other subscales to be recorded only at the visit)
- Intercourse details (to be recorded daily during the screening period)
- Dilator size 6 insertion details (to be recorded weekly during the screening period)
- PGI-S (to be recorded at the visit, and 1 week prior to the Baseline Visit)
- Q-tip test
- Dilator test
- Record:
  - Prior and concomitant medications/therapies (including pain rescue medication) administered within 28 days before the Screening Visit
  - Prior pelvic floor physical therapy or sex therapy received in the past 2 years prior to the planned Baseline
  - Treatment for anterior vestibular pain
  - Prior treatment with any BTX within the last 1 year
  - Prior and concomitant nondrug therapies and surgical procedures administered within 28 days before the Screening Visit
  - Use of any experimental new drug or device within past 4 weeks prior to the planned Baseline.
- Collection of AEs (since the signature of the informed consent)
- Instructions on patient diary completion.

Following confirmation of eligibility of the subject for the study and confirmation that the recruitment is still open in the cohort/group, subjects will be randomised and allocated to one of the dosing groups specified in Section 3.7.2.

A subject can be rescreened once, if all eligibility criteria were met but the subject was not enrolled due to any of the following, and twice due to ANY of the following conditions if they had to stop the first screening period due to COVID-19:

- Cohort recruitment being complete by the time the subject was eligible,
- If the subject had a UTI or vaginal infection at first screening and has received adequate treatment leading to complete resolution of the infection,
- If the subject failed screening due to a selection criterion that was removed from the previous version of the protocol. If the subject failed screening due to a selection criterion that was modified, she should have fulfilled the new criterion at the time of the first screening to be able to be rescreened. In these situations, the subject may only be rescreened once the new amended protocol has been approved by the IRB.

Rescreened subjects will sign a new informed consent form and a new subject number will be allocated. All screening assessments need to be repeated for the rescreened subject.

Each investigator will maintain a record of all subjects screened (i.e. who signed the informed consent form) and enrolled (i.e. who was given a randomisation number) into the study. Records up to the time of premature termination should be completed. In the event that the subject was not receiving IMP, the primary reason will be recorded.

### **5.2.2 Procedures During Double-Blind Period – Treatment Cycle 1 (Stage 1 + Stage 2)**

#### **5.2.2.1 Baseline Visit (Day 1)**

The following procedures will be performed prior to the administration of study treatment:

- Eligibility check (inclusion/exclusion criteria)
- PGI-S (to be recorded 1 week prior to the visit and at the visit)
- mFSFI (pain to be recorded 1 week prior to the visit and at the visit; other domains to be recorded only at the visit)
- Relationship/partner status (to be recorded weekly from 2 weeks prior to the visit and at the visit)
- mVPAQ (pain and life interference to be recorded 1 week prior to the visit and at the visit; other subscales to be recorded only at the visit)
- PHQ-9
- SF-36
- Intercourse details (to be recorded daily from 2 weeks prior to the visit)
- Dilator size 6 insertion details (to be recorded weekly from 2 weeks preceding the visit; assessment on the day of the visit should be avoided)
- Dilator test
- Measurement of pelvic floor muscle pressure (in all subjects in Stage 1 up to 400 U and in a subset of subjects in Stage 2 (i.e. in subjects who have never had a vaginal delivery (including attempted vaginal delivery), and at study sites that were provided a perineometer))
- Review of AEs
- New or changed concomitant medications/nondrug therapies
- Randomisation.

Once these procedures have been performed, the study treatment will be injected as described in Section [6.2.2](#).

Following injection, subjects will be observed at the study centre for at least 30 minutes.

#### **5.2.2.2 Week 2 – Telephone Contact (Day 15 ±3 days)**

The following procedures will be performed at this telephonic contact:

- Review of AEs
- New or changed concomitant medications/nondrug therapies.

#### **5.2.2.3 Week 6 Visit (Day 43 ±5 days)**

The following procedures will be performed:

- PGI-S (to be recorded 1 week prior to the visit and at the visit)\*
- PGI-C (to be recorded 1 week prior to the visit and at the visit)\*

- mFSFI (pain to be recorded 1 week prior to the visit and at the visit; other domains to be recorded only at the visit)\*
- Relationship/partner status (to be recorded weekly from 2 weeks prior to the visit and at the visit)\*
- mVPAQ (pain and life interference to be recorded 1 week prior to the visit and at the visit; other subscales to be recorded only at the visit)\*
- Intercourse details (to be recorded daily from 2 weeks prior to the visit)\*
- Dilator size 6 insertion details (to be recorded weekly from 2 weeks preceding the visit; assessment on the day of the visit should be avoided)\*
- Urine test for illicit drugs
- Dilator test
- Measurement of pelvic floor muscle pressure (in all subjects in Stage 1 up to 400 U and in a subset of subjects in Stage 2 (i.e. in subjects who have never had a vaginal delivery (included attempted vaginal delivery), and at study sites that were provided a perineometer to assess pelvic floor muscle pressure))
- CGI
- Review of AEs\*
- New or changed concomitant medications/nondrug therapies\*
- Subject interviews (every effort should be made to conduct the interview within 2 weeks of the subject's Cycle 1-Week 6 visit in Stage 2).

#### 5.2.2.4 Week 12 Visit (Day 85 +14 days)

The following procedures will be performed:

- mFSFI (pain to be recorded 1 week prior to the visit and at the visit; other domains to be recorded only at the visit)\*
- Relationship/partner status (to be recorded weekly from 2 weeks prior to the visit and at the visit)\*
- mVPAQ (pain and life interference to be recorded 1 week prior to the visit and at the visit; other subscales to be recorded only at the visit)\*
- PHQ-9\*
- SF-36\*
- PGI-S (to be recorded 1 week prior to the visit and at the visit)\*
- PGI-C (to be recorded 1 week prior to the visit and at the visit)\*
- Intercourse details (to be recorded daily from 2 weeks prior to the visit)\*
- Dilator size 6 insertion details (to be recorded weekly from 2 weeks preceding the visit; assessment on the day of the visit should be avoided)\*
- Blood sampling (nonfasting) for haematology and biochemistry\*\*
- Dilator test
- Measurement of pelvic floor muscle pressure (in all subjects in Stage 1 up to 400 U and in a subset of subjects in Stage 2 (i.e. in subjects who have never had a vaginal delivery (included attempted vaginal delivery), and at study sites that were provided a perineometer to assess pelvic floor muscle pressure))
- CGI

- Review of AEs\*
- New or changed concomitant medications/nondrug therapies\*.

\*\*In the event of a remote visit being required, blood sampling should be performed as soon as onsite visit resume and prior to the Week 18 Visit (as much as possible) and recorded as an unscheduled visit.

Once these procedures have been performed, the need for retreatment will be assessed as described in Section 3.7.3:

- Subjects eligible for retreatment will complete the remaining End of Cycle 1 assessments and enter the treatment cycle 2 (open-label, see Section 5.2.3.1) on the same day or once the DRC has confirmed the dose of the next cohort;
- Subjects not eligible for retreatment will perform an Additional Visit 6 weeks later (see Section 5.2.2.5).

In the event of a remote visit being required, subjects should not receive re-treatment with Dysport until onsite visits resume.

#### 5.2.2.5 Weeks 18, 24, 30 and/or 36 – Additional Visits (Day 127, 169, 211 and/or 253 ±14 days)

The following procedures will be performed:

- PGI-S (to be recorded 1 week prior to the visit and at the visit)\*
- PGI-C (to be recorded 1 week prior to the visit and at the visit)\*
- mFSFI (pain to be recorded 1 week prior to the visit and at the visit; other domains to be recorded only at the visit)\*
- Relationship/partner status (to be recorded weekly from 2 weeks prior to the visit and at the visit)\*
- mVPAQ pain and life interference subscales (to be recorded 1 week prior to the visit and at the visit)\*
- mVPAQ other subscales (at Week 24 and Week 36 only)\*
- PHQ-9 (at Week 36 only)\*
- SF-36 (at Week 36 only)\*
- Intercourse details (to be recorded daily from 2 weeks prior to the visit)\*
- Dilator size 6 insertion details (to be recorded weekly from 2 weeks preceding the visit; assessment on the day of the visit should be avoided)\*
- Dilator test
- Measurement of pelvic floor muscle pressure (in all subjects in Stage 1 up to 400 U and in a subset of subjects in Stage 2 (i.e. in subjects who have never had a vaginal delivery (included attempted vaginal delivery), and at study sites that were provided a perineometer to assess pelvic floor muscle pressure))
- CGI
- Review of AEs\*
- New or changed concomitant medications/nondrug therapies\*.

Once these procedures have been performed, the need for retreatment will be assessed as described in Section 3.7.3:

- Subjects eligible for retreatment will complete the remaining End of Cycle 1 assessments and enter the treatment cycle 2 (open-label, see Section 5.2.3.1) on the same day or once the DRC has confirmed the dose of the next cohort;
- Subjects not eligible for retreatment will perform an Additional Visit, every 6 weeks until they are eligible for retreatment or until they reach Week 36 visit. If eligible for retreatment at Week 36, subjects will perform the same assessments as described above for retreatment. If not eligible for retreatment at Week 36, subjects will perform the EOS Visit on the same day and complete the remaining EOS evaluations (see Section 5.2.4).

In the event of a remote visit being required, subjects should not receive re-treatment with Dysport until onsite visits resume.

### **5.2.3 Procedures During Open-Label Period – Treatment Cycles 2 to 4 (Stage 1 + Stage 2)**

#### *5.2.3.1 Day 1 Visit (Treatment Visit)*

The following procedures will be performed prior to the administration of study treatment:

- Urine pregnancy test
- Urine test for illicit drugs
- Review of AEs (only if the visit is not on the same day as the last visit of the previous cycle)
- New or changed concomitant medications/nondrug therapies (only if Day 1 is not on the same day as the last visit of the previous cycle).

If the visit occurs more than 2 weeks after the last visit of the previous treatment cycle, the following procedures will be done:

- PGI-S (to be recorded 1 week prior to the visit and at the visit)
- PGI-C (to be recorded 1 week prior to the visit and at the visit)
- Relationship/partner status (to be recorded weekly from 2 weeks prior to the visit and at the visit)
- Intercourse details (to be recorded daily from 2 weeks prior to the visit)
- Dilator size 6 insertion details (to be recorded weekly from 2 weeks preceding the visit; assessment on the day of the visit should be avoided)
- Dilator test
- CGI.

Once these procedures have been performed, the study treatment will be injected as described in Section 6.2.2.

Following injection, subjects will be observed at the study centre for at least 30 minutes.

#### *5.2.3.2 Week 2 – Telephone Contact (Day 15 ±3 days)*

The following procedures will be performed at this telephonic contact:

- Review of AEs
- New or changed concomitant medications/nondrug therapies.

#### *5.2.3.3 Week 6 Visit (Day 43 ±5 days)*

The following procedures will be performed:

- PGI-S (to be recorded 1 week prior to the visit and at the visit)\*

- PGI-C (to be recorded 1 week prior to the visit and at the visit)\*
- Relationship/partner status (to be recorded weekly from 2 weeks prior to the visit and at the visit)\*
- Intercourse details (to be recorded daily from 2 weeks prior to the visit)\*
- Dilator size 6 insertion details (to be recorded weekly from 2 weeks preceding the visit; assessment on the day of the visit should be avoided)\*
- Urine test for illicit drugs
- Dilator test
- CGI
- Review of AEs\*
- New or changed concomitant medications/nondrug therapies\*.

#### 5.2.3.4 Week 12 Visit (Day 85 ±14 days)

The following procedures will be performed:

- PGI-S (to be recorded 1 week prior to the visit and at the visit)\*
- PGI-C (to be recorded 1 week prior to the visit and at the visit)\*
- Relationship/partner status (to be recorded weekly from 2 weeks prior to the visit and at the visit)\*
- Intercourse details (to be recorded daily from 2 weeks prior to the visit)\*
- Dilator size 6 insertion details (to be recorded weekly from 2 weeks preceding the visit; assessment on the day of the visit should be avoided)\*
- Dilator test
- CGI
- Review of AEs\*
- New or changed concomitant medications/nondrug therapies\*.

Once these procedures have been performed:

- If this visit occurs >36 weeks from Cycle 1 Day 1, subjects will perform the EOS Visit on the same day and complete the remaining EOS evaluations (see Section 5.2.4).
- If this visit occurs ≤36 weeks from Cycle 1 Day 1, the need for retreatment will be assessed as described in Section 3.7.3:
  - Subjects eligible for retreatment will enter the next open-label treatment cycle (open-label, see Section 5.2.3.1) on the same day or once the DRC has confirmed the dose of the next cohort;
  - Subjects not eligible for retreatment will perform an Additional Visit 6 weeks later (see Section 5.2.3.5).

In the event of a remote visit being required, subjects should not receive re-treatment with Dysport until onsite visits resume.

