#### Open-Label Period (Treatment Cycles 2-4)

For a given subject, the Dysport dose for treatment cycles 2, 3 and 4 will be based on the investigator's judgement (based on efficacy and safety).

- Treatment cycle 2: the Dysport dose can either be the Dysport dose assessed in the previous treatment cycle (double-blind period) for the current cohort or the Dysport dose of the following cohort (provided it has been approved by the DRC).

- Treatment cycles 3 and 4: the Dysport dose can either be the dose assessed in the previous treatment cycle, a lower dose or the dose of the following cohort (provided it has been approved by the DRC).

If any subject fulfils the retreatment criteria and needs a higher dose for treatment prior to the DRC having approved the next dose level, the subject can either accept the dose level currently on, or delay injection until the next dose level is approved by the DRC or withdraw from the study.

A subject can receive up to a maximum of 4 treatment cycles with Dysport. The last treatment cycle should last at least 12 weeks and should not be initiated after Week 36.

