### 3.8 Study Duration

This study will consist of a 14-day screening period (Stage 1 and Stage 2), a double-blind treatment period including treatment administration at Day 1 and a follow-up period of 36 to 48 weeks (calculated from the dosing at Day 1). From Week 12 onwards of the double-blind period, the subject may enter an open-label treatment period and receive up to three additional treatment cycles with Dysport administered at least 12 weeks apart (a maximum of 4 treatments including the one received in the double-blind period).

Individual subject participation in this study will be for a maximum of 54 weeks (Stage 1 and Stage 2):

- Screening: 2 weeks (plus 2 weeks window)
- Follow-up: a maximum of 48 weeks follow-up plus 2 weeks window period for the EOS Visit depending on the number of treatments administered and the treatment intervals.

The subject's participation in the study will be considered to have ended 36 to 48 weeks after the first dose, but not before 12 weeks have elapsed after the last dose.

The overall duration of the study, including Stage 1 and Stage 2 with a maximum allowed dose of 800 U, will be approximately 4 years. The study will be considered to have started when the first subject has provided signed informed consent. The study will be considered to have ended after the last subject has completed the EOS visit in the study.

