l Subject interviews on the dilator test to be conducted in Stage 2 by invitation until the target sample of 20 subjects is achieved. Every effort should be made to conduct the interview within 2 weeks of the subject's Cycle 1-Week 6 visit.

m The visit window will be from Day -28 to Day -11.

n To be performed in all subjects in Stage 1 up to 400 U and in a subset of subjects in Stage 2 (i.e. subjects who have never had a vaginal delivery (included attempted vaginal delivery), and at study sites that were provided a perineometer to assess pelvic floor muscle pressure).

\* Study assessments that can be performed remotely if a subject is unable to attend a site visit due to the COVID-19 pandemic, except for the Screening, Baseline and EOS/EWD visits.

\*\* In the event of a remote visit being required, blood sampling should be performed as soon as onsite visit resume and prior to the Week 18 Visit (as much as possible) and recorded as an unscheduled visit.

Table 3 Study Procedures and Assessments – Open-Label Treatment Period

Study Procedures and Assessments	Open-Label Treatment Period Cycles 2 to 4						EOS / EWD
	V9, V13, V17	V10, V14, V18	V11, V15, V19	V12, V16, V20	Additional Visits [b]		
Visit Day/Week No.	Day 1 [a]	Week 2 (Day 15)	Week 6 (Day 43)	Week 12 [b] (Day 85)	Week 18 (Day 127)	Week 24 (Day 169)	Week 48 from Cycle 1 Day 1 (Day 337 from Cycle 1 Day 1) or Early withdrawal
Type of visit	Clinic	Telephone	Clinic	Clinic	Clinic	Clinic	Clinic
Visit Window		±3 days	±5 days	+14 days	±14 days	±14 days	±14 days
Prior/concomitant medication and non-drug therapies (incl. BTX and physiotherapy)*	X [c]	X	X	X	X	X	X
Adverse events*	X [c]	X	X	X	X	X	X
Urine pregnancy test	X [c]						X
Urine test for illicit drugs	X [c]		X				X
Clinical laboratory tests (non-fasting chemistry, haematology)**							X
Blood sample for antibodies**							X
PGI-S [i, j]*	X [d]		X	X	X	X	X
PGI-C [i, j]*	X [d]		X	X	X	X	X
eDiary relationship/partner status [e]*	X [d]		X	X	X	X	X
eDiary dilator insertion [k]*	X [d]		X	X	X	X	X
eDiary intercourse details [f]*	X [d]		X	X	X	X	X
Dilator test	X [d]		X	X	X	X	X
CGI	X [d]		X	X	X	X	X
Study drug administration	X [g]				X [h]	X [h]	X [h]
Assessment for retreatment							

AE=adverse event, BTX=botulinum toxin, CGI=clinical global impression, DRC=data review committee, EOS=end of study, EWD=early withdrawal, ICF=informed consent form, incl.=inclusive, NRS=numeric rating scale, PGI=patient global impression, SF-36=36-item short form survey, V=visit.

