#### **5.2.4 End of Study Visit or Early Withdrawal Visit**

The procedures to be carried out at the EOS Visit or EWD Visit are identical.

The following procedures will be performed at the EOS, or EWD visit (the procedures already performed on the same day at the previous study visit do not need to be repeated):

- mFSFI (pain to be recorded 1 week prior to the visit and at the visit; other domains to be recorded only at the visit; only if the EOS/EWD visit occurs during the double-blind period)
- mVPAQ (pain and life interference to be recorded 1 week prior to the visit and at the visit; other subscales to be recorded only at the visit; only if the EOS/EWD visit occurs during the double-blind period)
- PHQ-9 only if the EOS/EWD visit occurs during the double-blind period
- SF-36 (only if the EOS/EWD visit occurs during the double-blind period)
- PGI-S (to be recorded 1 week prior to the visit and at the visit)
- PGI-C (to be recorded 1 week prior to the visit and at the visit)
- Relationship/partner status (to be recorded weekly from 2 weeks prior to the visit and at the visit)
- Intercourse details (to be recorded daily from 2 weeks prior to the visit)
- Dilator size 6 insertion details (to be recorded weekly from 2 weeks preceding the visit; assessment on the day of the visit should be avoided)

- Urine pregnancy test
- Urine test for illicit drugs
- Blood sampling (nonfasting) for haematology, biochemistry and putative antibodies
- Dilator test
- CGI
- Review of AEs
- New or changed concomitant medications/nondrug therapies.

If the COVID-19 pandemic prevents subjects from coming to the site, EOS visits should be postponed until onsite visits resume.

Subjects who attend the EOS Visit will be considered to have completed the study.

Subjects with ongoing AEs or clinically significant laboratory test abnormalities (as determined by the investigator) will be monitored as described in Section 8.1.5 and Section 8.1.2.4, respectively.

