The psychometric properties of the dilator-induced pain Numeric Rating Scale (NRS), dilator size 6 insertion pain NRS, pain on intercourse NRS, mVPAQ, and modified Female Sexual Function Index (mFSFI) were to be evaluated using data collected from all subjects randomized in Stage 1 and Stage 2. The planned analyses of these data are described in the Psychometric Analysis Plan of validation study D-FR-52120-252. However, these analyses were cancelled following the decision to prematurely terminate the study.

1.3.5 ***Data review Committee and planned Analyses***

Data Review Committee

A DRC has been established to make recommendations for dose escalation and dose de-escalation or study termination decisions in Stage 1. It was planned that (a) if no subject reports a clinically significant AE (defined in the protocol section 3.1.1.1) in a cohort, the DRC will meet once all PVD2 and PVD1 evaluable subjects of a dose level have reached Week 6 to review the unblinded efficacy and safety data and decide the dose for the next cohort or proceed to Stage 2; (b) If any subject reports a clinically significant AE, then further enrolment into the cohort as well as retreatment in open label cycles at the current dose will be suspended and an ad hoc DRC meeting will be scheduled to review the data and make a recommendation with regards to further conduct of the cohort and of Stage 1.

Details related to DRC membership, responsibilities, procedures, role and remit are described in the DRC charter.

Early Study Termination Decision

Following the DRC meeting organized to review safety and efficacy data of cohorts 1 to 6 on the 16 OCT 2020, the DRC sent the following recommendation:

"No safety concerns noted in review of all available data. Efficacy cannot be assessed due to the small sample size of cohorts. The DRC would recommend that Stage 1 is not used to make an efficacy assessment, therefore there is no justification to increase the dose, nor to move to Stage 2."

Ipsen subsequently decided to close the study early and to run the final analysis based on available Stage 1 data. Subjects in the study are followed until 12 weeks after the last dose as described in the protocol section 3.9.

Final Analysis

The final analysis will be carried out once all subjects from cohorts 1 to 6 have completed end of study evaluation, after the database lock. All unblinded safety and efficacy data available at the time of the database lock will be analysed.

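### The open-label Week 12 and end-of-study visit windows contradict the protocol's own 12-week minimum after the last dose

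*Protocol*

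**What the plan says.** **The rule.** Protocol 3.8 ends participation 36 to 48 weeks after the first dose, "but not before 12 weeks have elapsed after the last dose". Sections 3.1.1 and 3.1.2 and the synopsis say the same in similar terms. Under the open-label headings of 3.7.2.1 and 3.7.2.2: "The last treatment cycle should last at least 12 weeks and should not be initiated after Week 36".

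**The open-label Week 12 visit.** The section heading is "5.2.3.4 Week 12 Visit (Day 85 ±14 days", and the table of contents repeats the two-sided window. The section then says: "If this visit occurs >36 weeks from Cycle 1 Day 1, subjects will perform the EOS Visit on the same day". Section 5.2.4 adds: "Subjects who attend the EOS Visit will be considered to have completed the study".

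**Table 3.** The EOS column is labelled "Week 48 from Cycle 1 Day 1 (Day 337 from Cycle 1 Day 1) or Early withdrawal". The window row reads, from the Week 6 entry through Week 12, Week 18, Week 24 and EOS/EWD, "5 days +14 days ±14 days ±14 days ±14 days". So Table 3 gives the open-label Week 12 visit +14 days only, and EOS ±14 days. For the double-blind Week 12 visit, Table 2 and section 5.2.2.4 agree on +14 days.

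**The concern.** The rule and the windows give different earliest dates for the end of study. A site that books visits from the section text or from the EOS column of Table 3, without checking back to 3.7.2 or 3.8, could close a subject before the 12 weeks have passed.

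EOS is where scheduled safety information stops. Adverse events are monitored until the end of study (8.1). In the open-label period, clinical laboratory tests and the antibody sample are scheduled only at EOS/EWD (Table 3), and the last urine pregnancy test is there too. Table 4 allows two antibody samples per subject and Tables 2 and 3 place them at screening and at EOS/EWD, so the EOS sample is the only one after treatment. It feeds the seroconversion summaries and the baseline-to-EOS shift table in SAP 3.9.6.

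**Working it through.** **Convention.** Injection is on Day 1 of the cycle, so day = 7 × week + 1, and time since injection = visit day − injection day.

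**Reproducing the protocol's own figures.** Week 12: 7 × 12 + 1 = Day 85. Week 36: 7 × 36 + 1 = Day 253. Week 48: 7 × 48 + 1 = Day 337. Maximum participation: 2 + 2 + 48 + 2 = 54 weeks. All four agree with the protocol.

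**Route 1: open-label Week 12 visit that becomes EOS (5.2.3.4).**
- Earliest visit under the section text: 85 − 14 = cycle Day 71; 71 − 1 = 70 days = 10.0 weeks after injection.
- Under Table 3 (+14 days only): 85 − 1 = 84 days = 12.0 weeks at the earliest, and 99 − 1 = 98 days = 14.0 weeks at the latest.
- A visit at 10 weeks becomes EOS if injection week + 10 > 36, that is, if the injection came after Week 26.
- Injection at Week 24 (Day 169): 169 + 70 = Day 239; (239 − 1)/7 = 34.0 weeks, so not EOS.
- Injection at Week 30 (Day 211): 211 + 70 = Day 281; (281 − 1)/7 = 40.0 weeks, so EOS, 10.0 weeks after the last dose.

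**Route 2: Week 48 EOS visit (Table 3).**
- Latest permitted start of the last cycle is Week 36, Day 253.
- Nominal EOS: 337 − 253 = 84 days = 12.0 weeks, exactly the minimum, so any minus tolerance breaches it.
- Earliest EOS in the window: 337 − 14 = Day 323; 323 − 253 = 70 days = 10.0 weeks.
- Latest EOS in the window: 337 + 14 = Day 351; 351 − 253 = 98 days = 14.0 weeks.

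**Shortfall.** 84 − 70 = 14 days; 14/84 = 16.7%.

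Route 1 rests on the text of 5.2.3.4 alone, because Table 3 does not allow an early Week 12 visit. Route 2 does not use that text, so it remains even if the ± in 5.2.3.4 is a slip.

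**The case against.** The strongest reply is that a visit window is a scheduling tolerance and does not cancel an explicit rule. The protocol treats retreatment this way: visits have windows, yet 3.7.3 still requires 12 weeks since the last treatment. This stands. A reader might infer that the protocol authorises 10 weeks of follow-up, but it does not. EOS at 10 weeks would fit a window and break the rule. What remains is that operative scheduling text and the rule disagree.

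Four other inferences are tempting, and the documents do not support them.
- *That the SAP sets its own 12-week minimum.* SAP 1.3.5 says "Subjects in the study are followed until 12 weeks after the last dose as described in the protocol section 3.9". That describes follow-up after early termination and relies on protocol 3.9, which asks only for all efforts. The firm minimum is in the protocol.
- *That the 48-plus-2-week wording in 3.8 and the synopsis makes the EOS window one-sided.* It states a maximum duration, and the upper end of Table 3's window (Week 50) agrees with it. Only the lower end conflicts, and it conflicts with the 12-week rule.
- *That the most heavily treated subjects are the ones affected.* What matters is when the last injection fell, not how many were given. A placebo subject first retreated at Week 36 (5.2.2.5) is in the same position after one Dysport dose. With intervals of at least 84 days and no start after Week 36, a fourth injection fits only on 1 + 3 × 84 = Day 253.
- *That safety reporting stops at an early EOS.* Suspected related events after completion must still be reported (8.1.6), as must pregnancies conceived and deaths occurring within 12 weeks of the last dose (8.1.7, 8.1.8). Ongoing adverse events are followed further (5.2.4, 8.1.5). What would be cut short is scheduled contact and sampling.

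**Conclusion.** The contradiction is real and the arithmetic exact. By either of two routes, a site following the printed window could hold EOS 70 days after the last injection, up to 14 days (16.7%) short of the 84 that the protocol sets as its minimum. Scheduled adverse event review would end earlier, and the final bloods, pregnancy test and sole post-treatment antibody sample would be taken earlier, by the same amount.

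This is an internal inconsistency, not a chosen shorter follow-up. The figure is the worst case within the windows and assumes that the site does not also apply 3.7.2 or 3.8. Nothing in the documents shows that any subject was closed early. The practical reach is limited: the study ended before Stage 2 and the SAP is descriptive, so the point bears on Stage 1 subjects still in follow-up and on reading the final EOS data.

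**What to change.** Reconcile three entries with one another and with the 12-week minimum stated in 3.1.1, 3.1.2, 3.7.2 and 3.8: the Week 12 window in 5.2.3.4, the Week 12 window in Table 3, and the EOS window in Table 3. Section text, table and electronic visit checks should then give one earliest EOS date. It is for the sponsor to settle what that date is.

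Table 3 has a single combined EOS/EWD column with one window. Give early withdrawal its own entry there, so that the correction does not constrain subjects who leave early.

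For the final analysis, any shortfall that did occur can be seen without new data. SAP 3.9.1 derives the length of a cycle not followed by retreatment as last attended visit minus injection date plus 1, so EOS at 70 days appears as 71 and the full 12 weeks as 85. Last-cycle values below 85 in subjects who completed should be listed separately from early withdrawals.

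The cost is a few corrected entries and the matching visit checks, with no added visits. There may be slightly less room in scheduling the last visit.
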